#### *2.1.3.1.3 Bone mineral density (BMD)*

BMD will be measured by DXA of both hips and the lumbar spine. T and Z scores, and bone mineral densities will be provided by the DXA report.

Centrally reviewed DXA data will be used to determine each patient's bone density category:

T-score Bone Density Categories:

- Normal: T-score  $> -1$
- Osteopenia:  $-2.5 < \text{T-score} \leq -1$
- Osteoporosis:  $\text{T-score} \leq 2.5$

Z-score Bone Density Categories:

- Normal: Z-score  $> -2$
- Below Normal: Z-score  $\leq -2$

Bone mineral density will be measured at screening and then yearly.

#### 2.1.3.1.4 Lytic lesions, osteonecrosis, fractures and infarcts

Lytic lesions, osteonecrosis, infarcts and fractures will be assessed on bone MRI and bone X-Ray. Bone MRI will be assessed at screening and then yearly. Bone X-Ray will be collected at screening and every 2 years.

##### Spine:

Infarction:

0 = Not Present

1 = Present

2 = Present, Unchanged

3 = Present, Larger

4 = Present, Smaller

NA = Not Available

NV = Not Viewable

Avascular Necrosis:

0 = Not Present

1 = Present

2 = Present, Unchanged

3 = Present, Larger

4 = Present, Smaller

NA = Not Available

NV = Not Viewable

Lytic lesion:

0 = Not Present

1 = Present

2 = Present, Unchanged

3 = Present, Larger

4 = Present, Smaller

NA = Not Available

NV = Not Viewable

Fracture:

0 = Not Present

1 = Present

2 = Present, Unchanged

3 = Present, Larger

NA = Not Available

NV = Not Viewable

##### Femur:

Infarction:

0 = Not Present

1 = Present

2 = Present, Unchanged

3 = Present, Larger

4 = Present, Smaller

NA = Not Available

NV = Not Viewable

Avascular Necrosis (represents infarction in the subchondral bone of the epiphysis):

0 = Not Present

1 = Present

2 = Present, Unchanged

3 = Present, Larger

4 = Present, Smaller

NA = Not Available

NV = Not Viewable

Dark Marrow (Bone Infiltration)

0 = Not Present

1 = Present

2 = Present, Unchanged

3 = Present, Larger

4 = Present, Smaller

NA = Not Available

NV = Not Viewable

Fracture

0 = Not Present

1 = Present

NA = Not Available

NV = Not Viewable

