9.1.4 Lytic lesions, osteonecrosis, fractures and infarcts

Lytic lesions, osteonecrosis, infarcts and fractures will be assessed on bone MRI and bone X-Ray.

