10.2.4.2 Imaging

- DXA of both hips and the lumbar spine
- MRI of entire bilateral femur and lumbar spine

- Liver and spleen MRI
- At the 2nd and 4th anniversaries only, X-Ray of femur and lumbar spine.

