#### **2.4.4.1.4 Lytic lesions, osteonecrosis, fractures and infarcts**

Total incidence of new or worsening lytic lesions, new or worsening AVN, new or worsening infarctions and new fractures among all locations will be summarized since study entry until all the patients completed their 2-year follow-up period and at end of study. Summary statistics (N, mean, standard deviation, median, minimum and maximum) will be displayed by visit. Annual incidence rates and will also be calculated as total number of incidence divided by the total number of person-years. MRI and X-ray assessment result will be summarized separately.

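### The SAP totals lytic lesions over all locations but has no femoral lytic-lesion item, so as written this primary-endpoint component covers the spine only

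*SAP*

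**What the plan says.** Both documents make this group of findings one of the five skeletal manifestations that form the primary endpoint. Protocol 9.1.4 states: "Lytic lesions, osteonecrosis, infarcts and fractures will be assessed on bone MRI and bone X-Ray". It sets no limit by site. The annual imaging in Protocol 10.2.4.2 includes "MRI of entire bilateral femur and lumbar spine", and femoral and lumbar X-rays are added at the second and fourth anniversaries.

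SAP 2.1.3.1.4 then lists the items to be scored. The spine list has infarction, avascular necrosis, lytic lesion and fracture. The femur list has infarction, avascular necrosis, "Dark Marrow (Bone Infiltration" and fracture. Spinal fracture has a code "2 = Present, Unchanged" and a further code for a larger fracture. Femoral fracture has only Not Present and Present, besides NA and NV.

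The analysis in SAP 2.4.4.1.4 is "Total incidence of new or worsening lytic lesions, new or worsening AVN, new or worsening infarctions and new fractures among all locations", counted from study entry. The annual rate is "calculated as total number of incidence divided by the total number of person-years". The same section adds that "MRI and X-ray assessment result will be summarized separately".

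**The concern.** The analysis asks for a quantity that the listed variables cannot supply. Both femurs are imaged and the endpoint is labelled as covering all locations, but the femur list has nowhere to record a lytic lesion. A programmer who follows the SAP will total the spine item alone and print it under the wider label. A reader of the report could then take a low count as evidence about the femurs, where the listed items did not score this finding.

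What is at stake is the meaning of one primary-endpoint component and its annual rate. The study is descriptive, so no error rate, power or sample size is affected. The primary objective is long-term skeletal response, however, and an item that was not read cannot be recovered by a later analysis.

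The femoral fracture coding raises a smaller question. At any single visit a new fracture and a persisting one carry the same code, and neither document says how a new one is to be identified.

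**Working it through.** The plan states no figure for this component, so there is none to reproduce. The check sets the sections side by side.

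**Step 1. Items listed against items analysed** (SAP 2.1.3.1.4 and 2.4.4.1.4)

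| Finding | Spine item | Femur item | Counted in the incidence analysis |
|---|---|---|---|
| Infarction | 0–4, NA, NV | 0–4, NA, NV | yes, new or worsening |
| Avascular necrosis | 0–4, NA, NV | 0–4, NA, NV | yes, new or worsening |
| Lytic lesion | 0–4, NA, NV | none | yes, new or worsening |
| Dark marrow | none | 0–4, NA, NV | no |
| Fracture | 0–3, NA, NV | 0–1, NA, NV | yes, new only |

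The one analysed finding without a femoral item is the lytic lesion.

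**Step 2. Could another variable fill the gap?**
- The femoral bone marrow burden items in SAP 2.1.3.1.2 are T1 signal, T2 signal and sites of involvement. They measure infiltration.
- Protocol 10.1 keeps local image interpretations out of the clinical database, so site readings cannot be used.
- Protocol 11.4.2.1 asks for the same incidence without restricting it to the spine, and Protocol 9.5.1 says that bone MRI can detect lytic lesions. The images exist and the endpoint covers them; the variable is missing.
- Neither code list names its modality, although MRI and X-ray are to be reported separately.

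**Step 3. Effect on the rate.** Let S be the new or worsening spinal lytic lesions, F the femoral ones and PY the person-years.
- Intended rate = (S + F) / PY.
- Rate obtainable from the listed items = S / PY.
- Proportion missed = F / (S + F).

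The documents give neither S nor F. The proportion is 0 if no femoral lesion arises and approaches 1 if nearly all do, so nothing narrower can be computed. For scale only, assume 32 patients who each contribute exactly 2 years: PY = 32 × 2 = 64. Each unrecorded femoral lesion then lowers the rate by 1/64 = 0.016 per person-year.

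**Step 4. Femoral fracture codes.** The sequences below are for screening, Week 52 and Week 104, the MRI reads available at the 2-year analysis.

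| True course | Codes | Changes from 0 to 1 |
|---|---|---|
| Present at screening, persists | 1, 1, 1 | 0 |
| New by Week 52, persists | 0, 1, 1 | 1 |
| New by Week 104 | 0, 0, 1 | 1 |
| Present at screening, plus a second new fracture in the same femur | 1, 1, 1 | 0 |

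A first new femoral fracture can be recovered from the planned codes. The first and last rows cannot be told apart. A read of NA or NV before the first code 1 also leaves the change undefined unless the SAP says which earlier read to compare with.

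**The case against.** The strongest reply is that both documents already require lytic lesions to be assessed on MRI and X-ray with no limit by site, and that the reader form itself is not in the documents. Dark marrow looks like an MRI item, so the femur list may not describe the X-ray form at all, and a reading charter might hold a femoral lytic-lesion item. This stands as a limit on the claim. One cannot say that femoral lytic lesions were never read, only that the SAP gives no variable for them and does not say which modality its lists cover. It does not remove the mismatch, because the SAP is the document that defines what is totalled.

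Three stronger readings are tempting, and the documents support none of them.
- A reader might put a percentage on the understatement by assuming what share of lesions arises in the femur. That only returns the assumed share.
- A reader might infer that a persisting femoral fracture will be counted again at every visit, giving up to four MRI records by Week 208. That requires treating each post-baseline Present as a new event, and SAP 2.4.4.1.4 says instead that "new or worsening infarctions and new fractures among all locations will be summarized since study entry". A fracture already present at screening shows no change from 0 to 1. At the 2-year analysis there are in any case only two post-baseline MRI reads.
- A reader might want the full set of spinal fracture codes for the femur. Only new fractures are counted, so a code for a larger fracture would feed no analysis.

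**Conclusion.** The SAP's item lists and its incidence analysis do not match on femoral lytic lesions. Followed as written, a named component of the primary endpoint is spine-only while labelled as covering all locations. This rests on the lists in SAP 2.1.3.1.4 being the full set of variables available to the analysis; a separate reader form could change the remedy but not the need to state it. The size of any understatement is unknown and could be zero. The other skeletal components are unaffected, since no composite is built.

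The fracture point is minor. The counting rule for a new femoral fracture is unwritten, and the case that the codes cannot show under any rule is a further fracture in a femur already coded Present. The correction is worth making because it changes what a reported primary result measures.

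**What to change.** 1. Add a lytic-lesion item to the femur list with the codes used for the spine (0–4, NA, NV), read by the same central readers on the images already planned.
2. State for each list whether it applies to MRI, X-ray or both.
3. If femoral lytic lesions were not read, relabel the endpoint and its annual rate as lumbar-spine lytic lesions.
4. Define a new femoral fracture as the first change from Not Present to Present relative to the last evaluable earlier read, skipping NA and NV. List separately any femur with no evaluable earlier read.
5. Add one code for a new fracture in a femur already coded Present.

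The cost is SAP wording, one more femoral item and one more fracture code on the reader form. No extra imaging, visits or patients are needed. If the reads are complete and femoral lytic lesions were not scored, items 2 to 4 still need only wording.

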#### **2.1.3.1.5 Bone biomarkers**

Bone biomarkers include:

- Total procollagen type 1 N-terminal propeptide (P1NP), a marker of bone formation.
- C-terminal telopeptide of type 1 collagen (CTX), a marker of bone resorption.
- MIP 1  $\beta$

These biomarkers will be measured at baseline and then every 6 months.

These markers will be measured by a central laboratory.

Results of centrally read assessments will be available to Investigators during or after the study depending on the assessment.

#### **2.1.3.2 Secondary efficacy endpoint(s)**

Blood levels of biomarkers of GD1 (chitotriosidase, plasma GL-1 and lyso-GL-1) will be evaluated at baseline and twice yearly. These markers will be measured in a central laboratory.

Measured values as well as absolute and percent changes from study baseline and eliglustat baseline will be summarized.

#### **2.1.3.2.1 Chitotriosidase Values**

Prior to being used in analyses, chitotriosidase values will be normalized using chitotriosidase genotyping information.

Chitotriosidase Genotype	Chitotriosidase value used in analyses
Normal	Value reported from the lab
Heterozygous	Value reported from the lab, multiplied by 2
Mutation	Homozygous BQL, set to missing (see Section 2.5.1 )

#### **2.1.3.3 Additional efficacy endpoint(s)**

Spleen volume and liver volume for non-URM patients will be evaluated at screening and every year by MRI. Hemoglobin and platelet results of non-URM patients will be assessed at screening and every half-year along with hematology laboratory test.

For URM patients, the frequency of spleen and liver volume MRI scan can be increased to every 3 months till Week 52. And the frequency of hematology and platelet test can be performed every 6 months till Week 52.

## 2.1.4 Safety endpoints

The safety analysis will be based on the reported adverse events (AEs) and other safety information, such as clinical laboratory data. The safety endpoints to be analyzed include:

### ***Observation period***

The observation period will be divided into 4 periods:

- The **pre-treatment period** is defined as the time from the signed informed consent to first dose of IMP administration in this study.
- The **treatment-emergent period** is defined as the time from the first administration of the IMP to the last administration of the IMP + 5 days. The treatment-emergent period includes the following 2 periods:
  - The **on-treatment period** is defined as the period from the first IMP administration to the last administration of the IMP + 1 day.
  - The **residual treatment period** is defined as the time from the last administration of IMP to the end of the treatment-emergent period.
- The **post-treatment period** is defined as the period from the end of treatment-emergent period.

The treatment-emergent adverse event (TEAE) observation period includes both on-treatment and residual treatment periods.

The on-study observation period is defined as the time from screening until the end of the study (defined as last protocol planned visit or the resolution/stabilization of all serious adverse events [SAEs] and adverse events of special interest [AESIs]).

### ***2.1.4.1 Adverse events variables***

#### ***Adverse event observation period***

- Pre-treatment adverse events are adverse events that developed or worsened or became serious during the pre-treatment period.
- Treatment-emergent adverse events (TEAEs) are adverse events that developed or worsened or became serious during the treatment-emergent period (treatment-emergent adverse event observation period).
- Post-treatment adverse events are adverse events that developed or worsened or became serious during the post-treatment period.

Continuous monitoring will be performed for (S)AEs and concomitant medications. Results of pregnancy testing for female patients of childbearing potential will be collected. Patients with an SAE or AESI should be followed until event resolution or when follow-up is no longer considered medically necessary, or the patient is lost to follow-up.

All adverse events (including SAEs and AESIs) will be will be coded to a lower-level term (LLT), preferred term (PT), high-level term (HLT), high-level group term (HLGT), and associated primary system organ class (SOC) using the version of Medical Dictionary for Regulatory Activities (MedDRA) currently in effect at Sanofi at the time of database lock.

Adverse events (including serious adverse events and adverse event of special interest) will be recorded from the time of signed informed consent until the end of the study.

Any SAE (including death) brought to the attention of the Investigator at any time after the end of the study for the patient and considered by him/her to be caused by the IMP with a reasonable possibility, should be reported to Global Pharmacovigilance department and will not be recorded in the clinical database.

Serious adverse events and adverse events of special interest (AESI) are defined in the protocol (refer to protocol Section 10.5.1.2 and 10.5.1.3). AESI will be identified and summarized based on CRF information, not standardized or customized MedDRA queries.

#### **2.1.4.2 Deaths**

The deaths observation period are per the observation periods defined above.

- Death on-study: deaths occurring during the on-study observation period
- Death on-treatment: deaths occurring during the treatment-emergent adverse event period

#### **2.1.4.3 Laboratory safety variables**

Clinical laboratory data consists of blood analysis, including hematology, clinical chemistry, and urinalysis. Clinical laboratory values after conversion will be analyzed into standard international units and international units will be used in all listings and tables.

Blood samples for clinical laboratories will be taken at visits described in the protocol or early termination unless otherwise specified. The laboratory parameters will be classified as follows:

- Hematology
  - **Red blood cells and platelets and coagulation:** Red Blood Cells (RBC), Hemoglobin, Hematocrit, Platelet Count
  - **White blood cells:** White Blood Cells (WBC), Neutrophils, Eosinophils, Basophils, Lymphocytes, Monocytes
- Clinical chemistry
  - **Markers of liver synthetic function:** Albumin, Total Bilirubin
  - **Markers of hepatocellular damage and cholestasis:** alanine aminotransferase, aspartate aminotransferase, alkaline phosphatase, gamma glutamyl transferase
  - **Pregnancy test:** Serum  $\beta$ -human chorionic gonadotropin for all female patients of childbearing potential

- **HIV and Hepatitis screen:** Human immunodeficiency virus (HIV) , hepatitis B surface antigen, anti-hepatitis-C antibody
- Urine samples will be collected as follows:
  - **Urinalysis:** Urine pregnancy test.

Technical formulas are described in [Section 2.5.1](#).

#### **2.1.4.4 Vital signs variables**

No vital sign variables are collected in this study.

#### **2.1.4.5 Electrocardiogram variables**

No electrocardiogram and Holter assessment variables are collected in this study.

#### **2.1.4.6 Other safety endpoints**

Complete physical exam and complete neurological exam with ocular motility test will be performed. Height and weight will be monitored as well.

### **2.1.5 Pharmacokinetic variables**

Although PK samples are not scheduled, unscheduled PK samples may be collected in individual. There is no planned analysis for these PK samples.

#### **2.1.6 Quality-of-life endpoints**

Patients' quality of life (Short Form-36 Health survey) will be evaluated at baseline and twice yearly. Total 8 scales including physical functioning, role-physical, bodily pain, general health, vitality, social functioning, role-emotional and mental health will be assessed based on SF-36. The two overall summary measures, physical component scale (PCS) and mental component scale (MCS), will be summarized from the 8 scales for quality of life assessment as well. SF-36 health survey is presented in [Appendix A](#).

## **2.2 DISPOSITION OF PATIENTS**

This section describes patient disposition for both patient study status and the patient analysis populations.

Screened patients are defined as any patient who met the study criteria and signed the informed consent.

For patient study status, the total number of patients in each of the following categories will be presented in the clinical study report using a flowchart diagram or summary table:

- Screened patients
- Screen failure patients and reasons for screen failure
- Treated patients
- Patients who completed the 2-year study period
- Patients who did not complete the 2-year study treatment period as per protocol
- Patients who completed the whole study period as per protocol
- Patients who did not complete study treatment period as per protocol
- Patients who discontinued study treatment by main reason for permanent treatment discontinuation

For all categories of patients, percentages will be calculated using the number of screened patients as the denominator. Reasons for treatment discontinuation will be supplied in tables giving numbers and percentages overall. Listing of permanent and temporary treatment discontinuation reasons by site and by patient will be provided respectively.

A patient is considered lost to follow-up at the end of the study if he/she is not assessed at the last protocol planned visit and failed to response to 3 attempts of contact via phone or registered letter.

All critical or major deviations potentially impacting efficacy analyses, inclusion, and drug-dispensing irregularities, and other major or critical deviations will be summarized in tables giving numbers and percentages overall and by site.

Additionally, the analysis populations for safety and efficacy will be summarized in a table by number of patients included in the study.

- Efficacy population
- Safety population
- Pharmacokinetics population

### **2.2.1 Randomization and drug dispensing irregularities**

Since the study is an open-label follow-up study and IVRS was not implemented, the randomization and drug dispensing irregularities is not applicable.

## **2.3 ANALYSIS POPULATIONS**

### **2.3.1 Efficacy populations**

Primary and secondary efficacy will be evaluated in the Full Analysis Set population (FAS) defined as all patients enrolled who receive at least 1 dose of eliglustat treatment in this study.

### 2.3.2 Safety population

Safety analyses will be performed on the Safety Set, which is equivalent to the FAS for this study.

### 2.3.3 Pharmacokinetic population

Pharmacokinetic (PK) population: a subset of safety population containing patients who have at least one PK sample taken. Patients will be analyzed in the treatment group corresponding to those defined in the safety population.

## 2.4 STATISTICAL METHODS

Analysis will be performed on safety and efficacy endpoints at 2 points in this study:

- After the last patient enrolled has completed 2 years of treatment (two-year analysis period)
- At the study completion

Both efficacy and safety results will be calculated both in reference to study entry (study period) and to first eliglustat treatment (eliglustat treatment period). Because patients will enter this study having been treated with eliglustat for various durations, two baselines will be used:

- Study baseline, defined as status at study entry, which is the last non-missing value before the first dose of eliglustat of this study; and
- Eliglustat baseline, defined as status at first dose of eliglustat in the previous Phase 2 or Phase 3 studies. The definition of eliglustat baseline should be the last non-missing value prior to first dose of eliglustat in prior studies.

The eliglustat baseline can only be obtained if the assessments in EFC13781 study and the previous studies are comparable. Assessment method, location, parameters, result evaluation, etc should be considered for comparability check if applicable. In addition, eliglustat baseline definition of hemoglobin and platelet for Phase 2 and ENCORE study were defined separately in [Section 2.5.2](#).

### 2.4.1 Demographics and baseline characteristics

Continuous data will be summarized using the number of available data, mean, standard deviation (SD), median, minimum and maximum in overall group. Categorical and ordinal data will be summarized using the number and percentage of patients in overall group.

Parameters will be summarized on the full analysis population analyzed in the overall group to which they were enrolled.

Parameters described in [Section 2.1.1](#) will be summarized in overall treatment groups using descriptive statistics.

